2.12.3 Soluble Biomarker

All biomarker data, including cytokines and other markers of inflammation implicated in the severity of COVID-19, will be summarized and visualized (including spaghetti plots, boxplots and mean plots with SD) by treatment for Day 1, Day 3, Day 8, Day 15 Day 29 and Day 91. Changes from baseline to values at each time point will be summarized for each Part by treatment.

[REDACTED]

[REDACTED]

[REDACTED]

[REDACTED]

[REDACTED]

2.14 Interim analysis

Part A

No interim analysis will be performed for the efficacy evaluation. Analysis of primary endpoint will be carried out when all patients have completed the Day 29 visit (or withdrawn prematurely) and have viral load data up to Day 8. Final analyses of part A will occur when all patients have completed Day 91 visit (or withdrawn prematurely). However, analyses of primary endpoint will not be repeated.

For the Part A primary analysis a cut-off date will be applied. All available data up to the cut-off date will be included in the analysis. The cut-off date is defined as the date when the last patient completed Day 29 visit or discontinued prematurely.

At time of primary analyses not all data up to the cut-off date will be available. Incomplete data are expected for

- Viral load data beyond Day 8.
- SARS-CoV-2 IgM / IgG antibodies data for Day 91
- Anti-SARS-CoV-2 neutralizing antibody test data – no data will be available

[REDACTED]

- PK data beyond Day 8

[REDACTED]

- Serum biomarker data – any visit

If not stated otherwise in the respective section, all analyses will be included in the Part A primary analyses. Analyses will include all available data.

Part B

There will be one interim analysis after 50% of patients complete Day 29 and one final analysis after at least 1717 patients have completed Day 91. The interim analysis permits early stopping due to efficacy controlling overall type I error rate. The interim analysis upper stopping bound in Z scale is 2.963 (corresponding to alpha is 0.03).

3 Sample size calculation

3.1 Primary endpoint(s)

Part A

In Documentation for the EUA for emergency use of casirivimab and imdevimab, issued 21 Nov 2020, it is shown that the treatment effect in time-weighted change from baseline (Day 1) to Day 8 of \log_{10} SARS-CoV-2 viral load in nasopharyngeal swabs was -0.36 for the overall population and -0.68 for the subgroup of patients with at least 10^7 copies at baseline and the estimated standard deviation was between 1.0 and 1.2.

Assuming the published evidence to be predictive over 8 days, a sample size of at least 100 patients per treatment group, for a total of 400 patients, would have at least 80% power (minimum power over the considered candidate shapes) with a one-sided Type I error rate of 0.10 to detect a dose-response trend versus placebo using MCP-Mod to select the smallest dose for consideration in the decision to move into Part B.

The power calculation given the range of operating characteristics (treatment effect: -0.36, -0.68, and standard deviation: 1, 1.1, 1.2) were performed based on MCP-Mod in R (Pinheiro 2006) and are presented in [Table 3.1-1](#).

Table 3.1-1 Power for Part A given a range of operating characteristics given 400 patients, 100 patients in each arm and a one sided significance level of 10%

Treatment Effect	Standard Deviation	Power (%)
-0.36	1	90.03
	1.1	85.25
	1.2	80.25
-0.68	1	99.98
	1.1	99.92
	1.2	99.73

Part B

Assuming the proportion of patients achieving the composite endpoint (of hospitalizations (\geq 24 hours of acute care) and/or emergency room visits, related to COVID-19, or death from any cause) up to Day 29 is 6.5% based on [Gottlieb et al \(2021\)](#) in the placebo group and 50% reduction with to 3.25%, a sample size of 1717 patients 1:1 randomized to two treatment groups provides at least 90% power that the primary analysis will be statistically significant using a two-sided log rank test with 5% significance level assuming that the survival rates are exponential. These results assume that the group sequential design has one interim analysis for

stopping the trial early for efficacy after 50% of patients complete Day 29 visit (two total analysis including final analysis) and the O'Brien-Fleming spending function is used to determine the efficacy test boundary.

Given possible enrichment for more severe COVID-19 cases, a range of operating characteristics were evaluated and presented in [Table 3.1-2](#).

Sample size calculations are performed in nQuery 8.4.1.0.

Table 3.1-2 Power for Part B given a range of operating characteristics

Total Sample Size	Placebo Event Rate (%)	Drug Event Rate (%)	Power (%)
1717	6.5	3.25	90.02
1588	7	3.5	90.01
1476	7.5	3.75	90.01
1380	8	4	90.04
1295	8.5	4.25	90.06
1217	9	4.5	90.03
1148	9.5	4.75	90.02
1086	10	5	90.02

3.2 Key secondary endpoint(s)

Not Applicable.

3.3 Other secondary endpoint(s)

Not Applicable.

4 Change to protocol specified analyses

Not applicable.

5 Appendix

5.1 Imputation rules

Any date incompletely reported is split into its day, month, and year components. In SAS, a numerical date value can only be defined if all these date components are known; incomplete dates are to be handled as text strings (character-type variables); as such, they could not be easily processed. An imputation rule for incomplete dates will be performed.

5.1.1 Study drug

Missing/partial start date/time or end date/time of study treatment will not be imputed.

5.1.2 AE date and hospitalization date imputation

This algorithm is expressed in the Variable Source Derivation column as **#IMPUTAEV(*event*)** where *event* is the partial start date of the AE. [Table 5.1-1](#) explains the notation used in the logic matrix. Please note that **missing start dates** will not be imputed. Note, if the imputed AE (or HO) start is after AE (or HO) end date, then set AE (or HO) start equal to AE (or HO) end date. Missing AE (or HO) end dates will not be imputed.

Table 5.1-1 Imputation logic for partial AE dates

	Day	Month	Year
Partial AE (or Concomitant Medication) Start Date	Not used	MON	YYYY
Treatment Start Date (TRTSDT)	Not used	TRTM	TRTY

The following matrix explains the logic behind the imputation.

	MON MISSING	MON < TRTM	MON = TRTM	MON > TRTM
YYYY MISSING	NC	NC	NC	NC
YYYY < TRTY	(D)	(C)	(C)	(C)
YYYY = TRTY	(B)	(C)	(A)	(A)
YYYY > TRTY	(E)	(A)	(A)	(A)

The following table is the legend to the logic matrix.

Relationship	
Before Treatment Start	Partial date indicates AE (or CM) start date prior to Treatment Start Date
After Treatment Start	Partial date indicates AE (or CM) start date after Treatment Start Date
Uncertain	Partial date insufficient to determine relationship of AE (or CM) start date to Treatment Start Date
Imputation Calculation	
NC / Blank Uncertain	No convention
(A) After Treatment Start or Uncertain	MAX(01MONYYYY, TRTSDT+1)
(B) Uncertain	TRTSDT+1
(C) Before Treatment Start	15MONYYYY
(D) Before Treatment Start	01JULYYYY
(E) After Treatment Start	01JANYYYY

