2.1.1.3 Study days

Study Day 1 (or Day 1 or reference start date) is defined as the day of first dose of study treatment.

All other study days are labeled as the number of days relative to Day 1. Therefore, for a particular date, study day will be calculated as follows:

- for dates on or after the date of first administration of study treatment:
Study day = Assessment date – date of study drug infusion + 1
- for dates prior to the date of first administration of study treatment:
Study day = Assessment date – date of study drug infusion

Moreover, duration of an event is calculated as:

Duration of an event = Event end date – event start date + 1.

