2.5.3 Handling of missing values/censoring/discontinuations

Part A

A combination of treatment policy and composite strategy will be used to handle the intercurrent events.

A treatment policy will be used to handle (1) post-treatment initiation of all antivirals (including convalescent serum, antiviral antibodies, and antiviral small molecules) and immunosuppressive medications; and, (2) post-treatment increase in dose of immunosuppressive medications, for the treatment or management of COVID-19, and a patient will be evaluated regardless of experiencing either of these intercurrent events.

A composite strategy will be used to handle (3) death from any cause and (4) COVID-19 related hospitalization. In the event a patient experiences death or COVID-19 related hospitalization, all values after the time of death/start of the COVID-19 related hospitalization for change from baseline in \log_{10} SARS-CoV-2 viral load will be set as the worst observed value based on observed values at each time point within each treatment arm independently.

All measurements in \log_{10} SARS-CoV-2 viral load missing for other reason than death or COVID-19 related hospitalization will be imputed using last observation carried forward (LOCF) approach.

Part B

A treatment policy will be used to handle (1) post-treatment initiation of all antivirals (including convalescent serum, antiviral antibodies, and antiviral small molecules) and immunosuppressive medications; and, (2) post-treatment increase in dose of immunosuppressive medications, for the treatment or management of COVID-19, and a patient will be evaluated regardless of experiencing either of these intercurrent events.

Patients who prematurely discontinue the study and whose outcomes after discontinuation are not ascertainable will have follow up censored at the date of last known status.

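### A COVID-19 hospitalisation whose day is still unknown at lock can be dated to Day 2, replacing swabs taken before the true admission in the Part A primary endpoint

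*SAP*

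**What the plan says.** SAP 5.1.2 is headed "AE date and hospitalization date imputation", and its text refers to AE (or HO) dates, so hospitalisation starts are in scope. Its matrix assigns rule (A), "MAX(01MONYYYY, TRTSDT+1", when the year and month equal those of treatment. It assigns rule (B), the day after infusion, when the month is missing and the year is the treatment year. For a later month, rule (A) gives the first of that month. The only cap is the end date: "if the imputed AE (or HO) start is after AE (or HO) end date, then set AE (or HO) start equal" to the end date. A start date with no year has no convention.

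SAP 2.1.1.3 numbers days as "Study day = Assessment date – date of study drug infusion + 1", so the day after infusion is Day 2.

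SAP 2.5.3 (and protocol 12.4.3) handles COVID-19 related hospitalisation by a composite strategy. It takes "all values after the time of death/start of the COVID-19 related hospitalization" and has them "set as the worst observed value based on observed values at each time point within each treatment arm independently". It makes no exception for imputed start dates or for swabs taken before the true admission.

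**The concern.** Taking the earliest plausible post-dose date is a cautious convention for adverse events, because it makes a doubtful event count as treatment-emergent. For this endpoint the start of a hospitalisation does a different job: it decides which viral loads are kept and which are replaced by an extreme value. A start on Day 2 comes before every post-baseline swab in the endpoint. A patient who gave outpatient swabs on Days 3 and 5 and was admitted later would lose both measurements, although those visits show that the imputed date is wrong.

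No planned analysis would reveal this. The jump-to-reference analysis in SAP 5.7.1 repeats the same composite handling. The repeated-measures model follows the primary analysis for intercurrent events. SAP 2.5.5 carries the primary estimand and missing-data plan into the supportive analyses.

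**Working it through.** **The plan's own figure.** Inputs are in protocol 12.8.1 and SAP 3.1: 100 patients per arm, doses 0, 75, 225 and 600 mg, the five candidate shapes, one-sided 10%, effects of 0.36 and 0.68, SD 1.0, 1.1 and 1.2. A multiple contrast test with optimal contrasts, a simulated critical value of 1.685 and the minimum power over shapes gives:

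| Effect | SD 1.0 | SD 1.1 | SD 1.2 |
|---|---|---|---|
| 0.36, plan | 90.03% | 85.25% | 80.25% |
| 0.36, recomputed | 90.15% | 85.41% | 80.39% |
| 0.68, plan | 99.98% | 99.92% | 99.73% |
| 0.68, recomputed | 99.99% | 99.92% | 99.74% |

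The power table reproduces. It is not in dispute here and only fixes the scale.

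**Date rule.** The first of the treatment month is never later than the infusion date, so rule (A) within that month always returns infusion + 1. Applied to all 365 infusion dates of a year, it returned Day 2 every time. With infusion dates spread evenly over the year, a true Day 6 admission falls in the treatment month for 84% of them and a true Day 9 admission for 74%.

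**Weights.** With nominal Days 1, 3, 5 and 8 and a change of zero at baseline, the SAP 2.5.1 formula is

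[0.5(0 + Y3)·2 + 0.5(Y3 + Y5)·2 + 0.5(Y5 + Y8)·3] / 7 = (2·Y3 + 2.5·Y5 + 1.5·Y8) / 7.

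Days 3 and 5 together carry 4.5/7 = 64%. Day 8 carries 1.5/7 = 21%.

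**Size for one patient.** The documents give no visit-level SD; I assume 1.2 to 2.0 log10. The largest of about 100 normal values lies about 2.5 SD above the mean. I also assume the patient's real values sit at the arm mean. The shift is (wrongly replaced weight) × 2.5 × SD, and dividing by 100 gives the change in the unadjusted arm mean:

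| True admission | Wrongly replaced | Weight | Patient shift | Arm-mean shift |
|---|---|---|---|---|
| Between Day 3 and Day 5 swabs | Day 3 | 2/7 | 0.86 to 1.43 | 0.009 to 0.014 |
| Between Day 5 and Day 8 swabs | Days 3, 5 | 4.5/7 | 1.93 to 3.21 | 0.019 to 0.032 |
| After Day 8 swab | Days 3, 5, 8 | 6/7 | 2.57 to 4.29 | 0.026 to 0.043 |

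**Worked patient.** Take real changes of −1, −2 and −3, and an arm-worst change w of 0, 1 or 2 at every visit. If the true admission was between the Day 5 and Day 8 swabs, the endpoint should be (−7 + 1.5w)/7 = −1.00, −0.79 or −0.57. Dated to Day 2 it is 6w/7 = 0.00, 0.86 or 1.71, a shift of 1.00, 1.64 or 2.29. If the true admission was after Day 8, the endpoint should be −11.5/7 = −1.64, and the shift is 1.64, 2.50 or 3.36. The arm mean moves by 0.010 to 0.034.

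**Against sampling error.** The standard error of a difference between two arms is SD × √(2/100) = 0.14 to 0.17 for SD 1.0 to 1.2. One misdated patient therefore moves it by between 0.009/0.17 = 0.05 and 0.043/0.14 = 0.3 standard errors.

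**Day 29 window.** Infusion on 10 September makes 1 October Day 22 and 8 October Day 29. An admission known only to be in October is set to 1 October and counts as an event, although 9 to 31 October would fall outside the window.

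**The case against.** The strongest reply is that the link is inferred. SAP 5.1.2 describes its argument as the partial start date of the AE, its table title and legend do not mention hospitalisations, and SAP 2.5.3 does not refer to it. Imputed hospitalisation dates may be wanted only for other outputs. This stands as a caution. But the section heading and the end-date cap name hospitalisations, and the SAP supplies no other start for a partial date.

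The second reply is that the trigger is guarded against. An admission for deterioration is an SAE (protocol 10.1.2), reportable within 24 hours with follow-up (10.1.3). Missing values are queried (11.2), and SAE documentation and primary-variable data are fully verified (11.3). This stands: few partial admission dates should survive to lock. An admission truly on Day 2 is also dated correctly.

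A reader might infer three stronger things that the documents do not support:

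- **Many patients are exposed.** Applying the Part B planning rates to Part A gives 100 × 6.5% + 300 × 3.25% = about 16 events. That count includes emergency room visits, which trigger no replacement, and runs to Day 29. The SAP's document history expects very few events in Part A.
- **Most October admissions in the example are miscounted.** Eight of 31 days lie inside the window, but days are not equally likely. Protocol 1.1 places dyspnoea in progressing patients at about Days 4 to 10 of illness, so early October is more likely than an even spread implies.
- **Power or the conclusion is at risk.** The frequency of partial dates is not given, and the direction depends on the arm: misdating in placebo favours ensovibep, and misdating in an active arm works against it.

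**Conclusion.** The concern holds in a limited form and is minor. Read together, SAP 5.1.2 and 2.5.3 can replace genuine pre-admission swabs with the arm's worst values. This happens only if the hospitalisation is COVID-19 related, its date is still partial at lock, and the true admission came after one or more of the Day 3, 5 and 8 swabs. Under the assumed visit-level SD of 1.2 to 2.0 log10, each such patient moves a 100-patient arm mean by about 0.01 to 0.03 log10, and up to about 0.04 if the admission came after Day 8. That is small beside 0.36.

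The Day 29 effect is an uncertainty, not a demonstrated error: the rule settles in-window status when the true date is unknown. It bears on the Part A secondary endpoint and, if carried forward, on the Part B primary endpoint. SAP 2.7.3.1 says missing data for the Part A endpoint are not imputed, so the status of an event with an imputed date also needs stating. The case for acting is that a stated rule gives a wrong answer when triggered, and correcting it is cheap.

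**What to change.** For hospitalisations only, replace the AE rule in SAP 5.1.2. Set a partial start to the earliest date consistent with three things: the reported month and year, the hospitalisation end date, and documented outpatient contacts known to precede the admission. The start should be no earlier than the day after the last such contact. Visits after discharge and swabs taken in hospital must not count as contacts; otherwise the bound could push a true early admission too late. Keep every swab observed before the resulting date, and state in SAP 2.5.3 that this is the start date the composite strategy uses.

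Where Day 29 status or the replacement of an observed swab depends on the imputed date, query it before lock. If it stays unresolved, show the result both ways.

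The cost is a short SAP amendment, slightly more programming, and confirmation of outpatient status at the relevant visits for the few patients affected. The documents do not say that visit location is recorded, so this may need a site query.

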5.1.3 Concomitant medication and therapies date imputation

The notation used is in the logic matrix of [Table 5.1-2](#). Rules for imputing the medication start date:

1) Medication start date year value is missing:

- If the medication start date year value is missing and the question "Started prior to start of study medication" is answered with "Yes", the imputed medication start date is set to one day prior to treatment start date, if not after the medication end date. Thus the imputed medication start date will be the minimum of one day prior to treatment start date and the medication end date.
- If the medication start date year value is missing and the question "Started prior to start of study medication" is answered with "No", the imputed medication start date

is set to treatment start date + 1 day, if not after the medication end date. Thus the imputed medication start date will be the minimum of one day after treatment start date and the medication end date.

- 2) If the medication start date year value is less treatment start date year value, the medication started before treatment start. Therefore:
 - a) If the medication start year is less than treatment start year and the medication month is missing, the imputed medication start date is set to 01JulYYYY.
 - b) Else if the medication start year is less than the treatment start year and the medication month is not missing, the imputed medication start date is set to 15MONYYYY.
- 3) if the medication start date year value is greater than treatment start date year value, the medication started after treatment start. Therefore:
 - a) If the medication start year is greater than the treatment start year and the medication month is missing, the imputed medication start date is set to 01JanYYYY.
 - b) Else if the medication start year is greater than the treatment start year and the medication month is not missing, the imputed medication start date is set to 01MONYYYY.
- 4) If the medication start date year value is equal to treatment start date year:
 - a) If the medication start month is missing or the medication start month is equal to treatment start month, then the imputed medication start date is set to the minimum of one day prior to treatment start date and the medication end date if the question "Started prior to start of study medication" is answered with "Yes".
 - b) If the medication start month is missing or the medication start month is equal to treatment start month, then the imputed medication start date is set to the minimum of one day after treatment start date and the medication end date if the question "Started prior to start of study medication" is answered with "No".
 - c) Else if the medication start month is less than the treatment start month, the imputed medication start date is set to 15MONYYYY.
 - d) Else if the medication start month is greater than the treatment start month, the imputed medication start date is set to 01MONYYYY.

Table 5.1-2 Imputation logic for partial concomitant medication enddates

	Day	Month	Year
Partial Conmed. end Date	Not used	MON	YYYY
Last Contact Date (LASTDT)	Not used	LSTM	LSTY

The following matrix explains the logic behind the imputation.

	MON MISSING	MON < LSTM	MON = LSTM	MON > LSTM
YYYY MISSING	NC	NC	NC	NC
YYYY < LSTM	(C)	(A)	(A)	(A)

YYYY = LSTY	(B)	(A)	(B)	(A)
YYYY > LSTY	(C)	(A)	(A)	(A)

The following table is the legend to the logic matrix.

Relationship	
Before Last contact date	Partial date indicates CM end date prior to Last Contact Date
After Last contact date	Partial date indicates CM end date after Last Contact Date
Uncertain	Partial date insufficient to determine relationship of CM end date to Last Contact Date
Imputation Calculation	
NC / Blank Uncertain	No convention
(A) Before/After Last contact date	Last day MONYYYY
(B) Uncertain	LASTDT
(C) Before/After Last contact date	31DECYYYY

If the above logic is applied and the imputed end date is after the cut-off date, then the imputed end date will be replaced with the cut-off date.

5.2 Derivation of risk of progression to severe COVID-19 and/or hospitalization

High risk of disease progression as per protocol:

Patients will be considered “high risk” if they meet at least one of the following criteria:

- Have a body mass index (BMI) ≥ 35
- Have chronic kidney disease
- Have diabetes mellitus
- Have immunosuppressive disease
- Are currently receiving immunosuppressive treatment
- Are ≥ 65 years of age
- Are ≥ 55 years of age AND have
 - Cardiovascular disease, OR
 - Hypertension, OR
 - Chronic obstructive pulmonary disease/other chronic respiratory disease.

All patients not meeting the above high-risk criteria will be considered “not at high risk”.

Additional criteria for 'High risk' of disease progression as per FDA updated definition on May 19, 2021

- Adults with BMI between 25 kg/m² and 35 kg/m²
- Pregnancy
- Age < 55 and cardiovascular disease (including congenital heart disease) or hypertension, chronic lung diseases / other chronic respiratory disease
- Sickle cell disease

- Neurodevelopmental disorders (for example, cerebral palsy) or other conditions that confer medical complexity (for example, genetic or metabolic syndromes and severe congenital anomalies)
- Having a medical-related technological dependence (for example, tracheostomy, gastrostomy, or positive pressure ventilation (not related to COVID-19))

5.3 Derivation of baseline COVID-19 severity

Baseline COVID-19 severity will be calculated based on the FDA guidance ([CDER 2020b](#)). Derivation for severe or critical COVID-19 are not included as these patients will not be enrolled in the trial.

Mild COVID-19:

- No presence of dyspnea (as found in the eCRF); AND,
- Respiratory rate < 20 breaths/minute; AND,
- Heart rate < 90 beats/minute.
- AND no criterion for moderate or severe COVID-19

Moderate COVID-19:

- Presence of dyspnea with exertion (as found in the eCRF); OR,
- Respiratory rate 20 - < 30 breaths/minutes; OR,
- Heart rate 90 - < 125 beats/minute
- AND no criterion for severe COVID-19.

Severe COVID-19:

- Presence of dyspnea at rest (as found in the eCRF); OR,
- Respiratory rate \geq 30 breaths/minutes; OR,
- Heart rate \geq 125 beats/minute; OR
- Oxygen saturation SpO₂ \leq 93%

